5.5 Criteria for Taking a Participant Off Protocol Therapy

Duration of therapy will depend on individual response, evidence of disease progression and tolerance. In the absence of treatment delays due to adverse event(s), treatment may continue until one of the following criteria applies:

- Disease progression
- Intercurrent illness that prevents further administration of treatment
- Pregnancy
- Unacceptable adverse event(s)
- Participant demonstrates an inability or unwillingness to comply with the oral medication regimen and/or documentation requirements
- Participant decides to withdraw from the protocol therapy
- General or specific changes in the participant's condition render the participant unacceptable for further treatment in the judgment of the treating investigator
- EXCEPTION: patients deriving clinical benefit from study treatment may continue on therapy at the discretion of the treating investigator to bridge to next treatment even if there is evidence of progressive disease

Participants will be removed from the protocol therapy when any of these criteria apply. The reason for removal from protocol therapy, and the date the participant was removed, must be documented in the case report form (CRF). Alternative care options will be discussed with the participant.

An ODQ Treatment Ended/Off Study Form will be filled out when a participant is removed from protocol therapy. This form can be found on the ODQ website or obtained from the ODQ registration staff.

In the event of unusual or life-threatening complications, treating investigators must notify the Overall PI, [name], as soon as possible, at [contact], DFCI [name].

5.6 **Duration of Follow Up**

Once participants have completed study treatment they will be followed until initiation of new therapy, or until death, whichever occurs first. After cycle 24, subjects remaining on investigational therapy will be seen every 3 months in clinic for as long as they remain on study treatment. Subjects who discontinue acalabrutinib/venetoclax because they are in CR/CRi with MRD-negativity will be followed as per the study calendars in section 10. In these subjects, if no relapse is detected after 48 cycles of therapy, they may return to follow-up with a local

hematologist but will be followed by telephone for updates on disease progress and overall survival. Participants removed from treatment for unacceptable adverse events will be followed until resolution or stabilization of the adverse event, and/or until initiation of new therapy for their disease, whichever is longer.

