5.7 Criteria for Taking a Participant Off Study

Participants will be removed from study when any of the following criteria apply:

- Lost to follow-up
- Withdrawal of consent for data submission
- Start of new CLL-directed therapy
- Disease Progression
- Death

Participants will be removed from the protocol therapy when any of these criteria apply. The reason for removal from protocol therapy, and the date the participant was removed, must be documented in the case report form (CRF). Alternative care options will be discussed with the participant.

When a participant is removed from protocol therapy and/or is off of the study, the relevant Off-Treatment/Off-Study information will be updated in OnCore. This form can be found on the ODQ website or obtained from the ODQ registration staff.

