6.3 Acalabrutinib

Treatment with acalabrutinib should be held for any unmanageable, potentially study drug-

related toxicity that is Grade ≥ 3 in severity. Study drug may be held for a maximum of 28 consecutive days from expected dose due to toxicity. Acalabrutinib should be permanently discontinued in the event of a toxicity thought at least possibly due to acalabrutinib lasting > 28 days despite holding drug, unless reviewed and approved by the Overall PI. Any subject who permanently discontinues acalabrutinib prior to cycle 4 will no longer be eligible for any of the study drugs and will come off study treatment but continue to be followed as detailed in section 5.6. Any subject who discontinues acalabrutinib at cycle 4 or later may continue on the other study medications.

Dose Reduction Table

The actions in Table 11 below should be taken for the following toxicities if thought to be at least possibly related to acalabrutinib:

- Grade 4 ANC ($< 500/\mu$ L) for > 7 days (Neutrophil growth factors are permitted and use must be recorded on the case report form [CRF]).
- Grade 3 or higher platelet decreases in presence of significant bleeding.
- Grade 4 platelet decreases.
- Grade 3 or 4 nausea, vomiting, or diarrhea, if persistent for >7 days despite optimal antiemetic and/or anti-diarrheal therapy.
- Any other Grade 4 toxicity or unmanageable Grade 3 toxicity.

Table 11: Dose Modifications for Acalabrutinib

Occurrence	Action
1st - 2nd	Hold acalabrutinib until recovery to Grade ≤ 1 or baseline; may restart at
	original dose level
3rd	Hold acalabrutinib until recovery to Grade ≤ 1 or baseline; restart at one dose
	level lower (100 mg once daily)
4th	Discontinue acalabrutinib

Any changes to the dosing regimen must be recorded in the Dosage Administration CRF.

If acalabrutinib is reduced for apparent treatment-related toxicity, the dose need not be re-escalated, even if there is minimal or no toxicity with the reduced dose. However, if the subject tolerates a reduced dose of acalabrutinib for ≥ 4 weeks then the dose may be increased to the next higher dose level, at the discretion of the investigator. Such re-escalation may be particularly warranted if further evaluation reveals that the AE that led to the dose reduction was not treatment-related.

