7.3.1.3 Post-Study Adverse Events

For studies involving collection of survival data and extended follow-up after the end of the adverse event reporting period (defined as 30 days after the last dose of study drug), the investigator should report all deaths (regardless of cause) and any serious adverse event including development of cancer or a congenital anomaly in a subsequently conceived offspring of a female subject who participated in the study (including pregnancy occurring in the partner of a male study subject) that is believed to be related to prior exposure to study drug. Case Transmission Verification will be performed by both parties during this period to ensure successful transmission of single case reports.

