Adverse Event Evaluation	X	X	X	X	X	X	X	X	X	X	X	X	X	X	X	X	X	X	X	X	X	X	X	X	X
TLS Prophylaxis ⁸			X	X						X								X							
Peripheral Blood MRD Analysis ^{9, 16}										X												X		X	X
Adaptive ClonoSEQ MRD Analysis										X												X		X	X
Other correlative studies ¹⁰	X	X	X		X					X												X			X

¹ Only required in women of childbearing potential

² Unilateral bone marrow aspirate and/or biopsy required within 6 months of screening.

³ MRD assessment should be sent on marrow samples taken after cycles 3, 7, 15, and 24.

⁴ Marrow sample requested for correlative studies if bone marrow biopsy is done as standard of care, or as part of protocol schedule. Flow cytometry (lymphoma panel), karyotype, and FISH (CLL) should be performed on all bone marrow biopsies (FISH may be performed on either marrow or blood and is not required on both).

⁵ These baseline serologies may be completed within 4 weeks of initiation of therapy. For those patients who are either hepatitis B core antibody and/or hepatitis B surface antigen positive but HBV DNA negative, pharmacologic prophylaxis and monitoring of HBV DNA is required as detailed in section 5.4. HTLV serologic testing is not required but is strongly suggested if the treating clinician has a high suspicion for HTLV infection.

⁶ CBC with differential, hemoglobin, hematocrit, platelets

Off-study evaluation. Note: for IND/IDE trials, follow up visits or other contact are required in order to identify SAEs during the 30 days following the end of study treatment.

⁷ Calcium, Sodium, Potassium, Phosphorus, Chloride, Glucose, Magnesium, Albumin, AST, ALT, Creatinine, BUN, Bicarbonate, Total protein, Total bilirubin (and direct bilirubin if total Bilirubin is abnormal), Uric acid, LDH, Alkaline phosphatase

⁸ TLS prophylaxis will consist of allopurinol in subjects without a history of an adverse reaction to this drug, or an alternative anti-hyperuricemic agent.

⁹ Peripheral blood MRD analysis will be done by four color flow cytometry through a reference laboratory with a detection limit of 10⁻⁴ cells per leukocyte.

¹⁰ Baseline correlative studies may be obtained either at the screening visit or prior to study drug administration on C1D1.

¹¹ Only cycle days requiring outpatient visits or laboratory evaluations are listed. Provided that there is no evidence of TLS or adverse events, venetoclax dosing is continuous throughout this cycle at doses as specified in the treatment plan.

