⁵ Calcium, Sodium, Potassium, Phosphorus, Chloride, Glucose, Magnesium, Albumin, AST, ALT, Creatinine, BUN, Bicarbonate, Total bilirubin (and direct bilirubin if total Bilirubin is abnormal), Uric acid, LDH, Alkaline phosphatase

⁶ Peripheral blood MRD analysis will be done by four color flow cytometry through a reference laboratory with a detection limit of 10⁻⁴ cells per leukocyte.

⁷ Subjects with CR/CRi and MRD-negativity at C16D1 who choose to discontinue therapy will be seen in clinic on cycles 19, 22, and 25 and then every three cycles for 2 years (i.e. through cycle 48). If relapse is detected by PB flow cytometry at any of these time points, subjects will be re-staged with CT scan (if not done in the three months prior) and bone marrow biopsy (if not done in the six months prior) and will resume acalabrutinib and venetoclax until progression / unacceptable toxicity per the follow-up schedule on the following page. If no relapse is detected by cycle 48, subjects who are no longer on study treatment may return to follow-up with a local hematologist but will be followed by telephone for updates on disease progress and overall survival.

⁸ If at the time of coming off study the subject is ≤2 weeks from coming off of therapy, the evaluations done at the off-treatment visit will suffice and need not be repeated. Follow-up data will be collected every three cycles until death, up to 5 years after the initial dosing.

⁹Bone marrow and peripheral blood samples sent to Mayo Clinic for MRD assessment are considered part of standard of care disease monitoring, not research.

Study Calendar for patients who **ARE NOT** in complete remission with MRD-negativity in the bone marrow and blood at cycle 16 evaluation OR who are in complete remission yet choose to continue therapy (Cycles 17 and beyond)

Cycle = 28 days	Cycle 19 (±14 days)	Cycle 22 (±14 days)	Cycle 25 ⁶ (±14 days)	Every 3 cycles until cycle 48 ⁷ (±14 days)	Clearance of MRD from the blood ⁸	Off Treatment	Off Study ⁹
Procedure		Day 1	Day 1				
Acalabrutinib	X	Daily o	dosing days 1-2	8X	X		
Obinutuzumab							
Venetoclax	X	Daily	dosing days 1-2	28X	X		
Medical history, physical exam, vital signs (weight, resp rate, HR, BP, temp, O ₂ sat), and ECOG Performance Status	X	X	X	X		X	X
Bone Marrow aspirate / biopsy / MRD assessment ^{1,2,10}			X		X		
CT scan (+/- 7 days)			X		X	X	X
Hematology ³ and Serum Chemistry ⁴	X	Х	X	X	X	X	X
Adverse Event Evaluation	X	X	X	X		X	X

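### Section 5.6 ends follow-up at new therapy while the Off Study notes of three calendars continue it to death (5-year cap); no text says which governs the 2- and 3-year OS data

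*Combined protocol and SAP*

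**What the plan says.** - **Section 5.6 (general rule).** After study treatment, patients are followed "they will be followed until initiation of new therapy, or until death, whichever occurs first". The only referral to the section 10 calendars is for patients who stop in MRD-negative CR/CRi. If those patients have not relapsed after cycle 48 they may return to a local hematologist and "will be followed by telephone for updates on disease progress and overall survival". The separate rule for patients stopping for adverse events also names new therapy as an end point and does not mention survival.
- **Section 5.7.** "Participants will be removed from study when any of the following criteria apply"; the list includes disease progression and "Start of new CLL-directed therapy". It does not say whether survival follow-up continues afterwards.
- **Section 10, the three calendars after cycle 16** (stopped in remission, continuing therapy, retreatment). Each has an Off Study note that opens "If at the time of coming off study the subject is" and ends by requiring follow-up data every three cycles for life, with a cap of five years from first dose.
- **Section 10, cycles 1-16 calendar.** As extracted, the only off-study text says that "follow up visits or other contact are required in order to identify SAEs during the 30 days following the end of study treatment".
- **Section 6.3.** A patient who permanently stops acalabrutinib before cycle 4 "will come off study treatment but continue to be followed as detailed in section 5.6".
- **Section 7.3.1.3.** For the period after adverse event reporting ends, investigators are asked to report deaths from any cause.
- **Endpoint.** Section 1.3 lists median, 2-year and 3-year OS. Section 13.2 allows up to three years after the last enrolment for 3-year OS. Section 13.6 uses Kaplan-Meier. Appendix B censors living patients at the date they were last known alive.

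**The concern.** Take a patient who starts another CLL therapy in year 2. Under 5.6, follow-up is finished. Under the calendar notes, contact continues for up to about three more years. The two rules give different dates last known alive, and Appendix B makes that date the OS censoring time.

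The patients affected are not a random subset, because they are the ones for whom treatment has failed. If they leave the risk set at new therapy and their later deaths are not captured, Kaplan-Meier treats their prospects as equal to those of patients still in remission, and OS is biased upward. Section 2.4 opens the trial to community sites, so different sites could apply different text.

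**Working it through.** **1. Does any other text settle it?** The plan has no figure to reproduce here, so the texts are set against each other first.

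- *Telephone contact.* It starts after cycle 48: 48 × 28 = 1,344 days = 3.68 years on schedule. That is past both OS landmarks.
- *Section 7.3.1.3.* It asks for deaths but schedules no contact with living patients, so it gives no date last known alive.
- *Early leavers.* The cycles 1-16 calendar covers the first 16 × 28 = 448 days = 1.23 years. Patients who leave in that time are outside the three calendars with the note, and section 6.3 sends some of them to 5.6.

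None of these says which rule governs.

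**2. Inputs for the size of the error.** The protocol gives no progression or survival rates for this regimen.

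- *PFS.* Section 2.2.1.16 reports 82% progression-free at 24 months on frontline venetoclax-obinutuzumab. Extended exponentially, 3-year PFS = 0.82^(3/2) = 0.7425, so the hazard of leaving the progression-free state is L = −ln(0.7425)/3 = 0.0992 per year.
- *Assumed:* death before progression d0 = 0.01 per year; death after progression d1 = 0.10 to 0.40 per year; mean time from progression to new therapy 0.5 year (rate 2 per year).

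**3. True OS.**

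OS(t) = exp(−Lt) + (L − d0)·[exp(−d1·t) − exp(−Lt)]/(L − d1)

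At t = 3 and d1 = 0.40: 0.7425 + 0.0892 × (0.3012 − 0.7425)/(0.0992 − 0.40) = 0.8735, or 87.3%. At d1 = 0.10 the result is 94.1%.

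**4. OS as estimated if collection stops at new therapy.** Patients still observed are those without progression, S0 = exp(−Lt), and those progressed but not yet on new therapy,

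SL = (L − d0)·[exp(−Lt) − exp(−(d1 + 2)t)]/(d1 + 2 − L).

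The observed hazard is h = (S0·d0 + SL·d1)/(S0 + SL), and the estimate is exp(−∫h) from 0 to t.

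| d1 | True 3-year OS | Estimated | Overstated by |
|---|---|---|---|
| 0.10 | 94.1% | 96.1% | 2.0 points |
| 0.40 | 87.3% | 93.5% | 6.1 points |

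The last column is taken before rounding.

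**5. Sensitivity.** Over a wider grid (3-year PFS 60-90%, d0 1-2%, d1 10-40%, same lag) the overstatement is 0.1 to 4.7 points at 2 years and 0.3 to 9.9 at 3 years. With a mean lag of 0.25 year the 3-year range is 0.4 to 12.4, and with 1 year it is 0.2 to 6.8.

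**6. Other ways a site might act.** If the calendar notes are followed, the error is zero. If deaths are still reported under 7.3.1.3 but living patients are censored at new therapy, every death counts while survivors leave the risk set early. A simulation over the step 5 grid then understates 3-year OS by 0 to 1.8 points.

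**7. Scale.** At 92% survival the binomial standard error is √(0.92 × 0.08/36) = 4.5 points for 36 patients and √(0.92 × 0.08/71) = 3.2 points for 71.

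**The case against.** The best defence is to read the texts in sequence. New therapy is itself an off-study trigger in 5.7, and the until-death notes begin at the point of coming off study. On that reading 5.6 describes on-study follow-up, and the notes describe what follows. Appendix B, the 3-year OS plan in 13.2 and the request for deaths in 7.3.1.3 all suggest that survival was meant to be tracked past new therapy. This reading is possible, and it is probably the intent. But it is not forced: the general sentence in 5.6 has no such qualification, and 5.6 refers only one group to the calendars.

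A reader might infer that the protocol has no survival follow-up rule at all. It does not support that, because three calendars state one. What is missing is precedence, and coverage of early leavers.

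A reader might also conclude that the cycles 1-16 calendar definitely lacks the note. That is uncertain. Its off-study text stands apart from the numbered footnotes with no matching column, so a column may have been lost in extraction.

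Finally, treating 5.7 as ending data collection at progression would raise the 3-year overstatement to as much as 16.2 points. That needs the most extreme corner of the wider grid and a reading of 5.7 that its text does not require, since leaving the study at progression is compatible with the calendar notes.

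**Conclusion.** The point stands as an unresolved conflict between 5.6 and the calendar notes, with a possible gap for patients who leave before cycle 17. It does not show that OS will be wrong, because both the size and the direction of any error depend on which text a site follows.

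If 5.6 is taken literally, 3-year OS is overstated by about 2 to 6 points under the section 2.2.1.16 extrapolation. That rests on a different regimen, constant hazards, an assumed six-month lag and assumed death rates. Cohort 2 is entirely TP53-aberrant, so its progression may be faster; the 60% end of the wider grid allows for that. The likely error is of the order of one standard error. It matters because it is systematic and avoidable.

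OS is secondary and descriptive, and the cycle 15 primary endpoint is untouched. This should be fixed, at modest priority.

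**What to change.** Reconcile 5.6 and 5.7 with section 10:

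- State that neither progression nor new CLL-directed therapy ends survival follow-up.
- State that survival status and the date last known alive are collected every three cycles until death, withdrawal of consent or five years from first dose, for all treated patients, including those who leave before cycle 17.
- Check the original PDF of the cycles 1-16 calendar, and add the same note there if it is absent.
- Leave the rules for giving and stopping therapy unchanged.

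The cost is a protocol revision with IRB approval (Appendix J), plus survival contacts for patients who leave early or start new therapy. The interval and cap are already in three calendars. It is best done soon, because survival dates may be hard to recover for patients already closed out under 5.6.

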5.7 Criteria for Taking a Participant Off Study

Participants will be removed from study when any of the following criteria apply:

- Lost to follow-up
- Withdrawal of consent for data submission
- Start of new CLL-directed therapy
- Disease Progression
- Death

Participants will be removed from the protocol therapy when any of these criteria apply. The reason for removal from protocol therapy, and the date the participant was removed, must be documented in the case report form (CRF). Alternative care options will be discussed with the participant.

When a participant is removed from protocol therapy and/or is off of the study, the relevant Off-Treatment/Off-Study information will be updated in OnCore. This form can be found on the ODQ website or obtained from the ODQ registration staff.

6. DOSING DELAYS / DOSE MODIFICATIONS

Dose delays and modifications will be made as indicated in the following table(s). Hematologic AEs will be graded as per the IWCLL Grading Scale for Hematologic Toxicities in CLL Studies (Appendix C). Nonhematologic AEs will be described and graded as per the revised NCI Common Terminology Criteria for Adverse Events (CTCAE) version 5.0. A copy of the CTCAE version 5.0 can be downloaded from the CTEP website http://ctep.cancer.gov/protocolDevelopment/electronic applications/ctc.htm.

Given that multiple drugs in this study can cause similar side effects, treating clinician discretion in consultation with the Principal Investigator can be used to decide which agent to dose reduce when patients experience a side effect that could be attributable to multiple drugs.

6.1 Venetoclax

Dose Reduction Table

The dose for venetoclax in this study is 400 mg QD (after intra-patient dose ramp-up). If known venetoclax toxicities such as tumor lysis syndrome, gastrointestinal adverse events, or neutropenia (as detailed in sections 6.1.2 and 6.1.3) are observed, dose reductions to the following dose levels for venetoclax may be utilized:

Table 3. Veliciociax De	ise reduction senema		
Dose at Interruption, mg	Restart Dose, mg ^a		
400	300		
300	200		
200	100		
100	50		
50	20		
20	10		
^a Continue the reduced dose for 1 week before			

Table 5: Venetoclax Dose Reduction Schema

Prophylaxis and Management of Tumor Lysis Syndrome

increasing the dose.

Upon initial treatment of CLL with venetoclax, there is a potential for TLS, especially in those with elevated lymphocyte count, bulky lymphadenopathy, and renal dysfunction. To mitigate the risk for TLS, all patients on this study will be restaged with CT scan prior to initiation of venetoclax on cycle 4 day 1 to assess for risk of TLS. Patients will be managed according to Table 6.

Table 6: Prophylaxis and Monitoring For TLS Syndrome in Patients Receiving Venetoclax

	Tumor Burden	, 	Prophylaxis	
		Hydration ^a	Antihyperuricemics	Monitoring ^{c,d} Setting and Frequency of Assessments
Low	All LN <5 cm AND ALC <25 x10 ⁹ /L Any LN 5 cm to <10 cm OR ALC ≥25 x10 ⁹ /L	Oral (1.5-2 L) and consider additional intravenous	Allopurinol ^b	Outpatient • Pre-dose, 6-8 hours post-dose, and 24 hours post-dose, on days where patient receives first dose of 20, 50, 100, 200, or 400mg • Consider hospitalization for patients with CrCl <80ml/min at first dose of 20 mg and 50 mg; see below for monitoring in hospital
High	Any LN ≥10 cm OR ALC ≥25 x10 ⁹ /L AND any LN ≥5 cm	Oral (1.5-2 L) and intravenous ^e	Allopurinol; consider rasburicase if baseline uric acid is elevated ^f	Inpatient: • Pre-dose, 4, 8,12 and 24 hours post doses of 20 and 50mg Outpatient: • At subsequent ramp-up doses as outlined above for low and medium risk patients

ALC = absolute lymphocyte count; LN = lymph node.

If any significant laboratory changes are observed within the first 24 hours after initiation of dosing, see Appendix E (Recommendations for Initial Management of Electrolyte Abnormalities and Prevention of Tumor Lysis Syndrome [TLS]), for additional laboratory assessments and management guidelines. If aggressive correction of electrolytes abnormalities was performed, the subsequent dose of venetoclax can only be given when electrolytes have been stable without any further treatment for approximately 24 hours.

^a Administer intravenous hydration for any patient who cannot tolerate oral hydration.

^b If possible start allopurinol or xanthine oxidase inhibitor about 3 days prior to initiation of venetoclax.

^c Evaluate blood chemistries (potassium, uric acid, phosphorus, calcium, and creatinine); review in real time. During the dose ramp-up period, the subsequent dose should not be administered until the 24 hours post-dose laboratory values are reviewed by the investigator.

 $^{^{\}rm d}$ All same-day laboratory assessments may be taken within ± 2 hour window, and 24 hour laboratory assessments within a ± 6 hour window, if necessary

 $^{^{\}rm c}$ Intravenous fluids should be given at 150-200 mL/hr starting the night before the first dose of 20 mg, with a target of approximately 1.5-2 L/day (or as clinically appropriate), and continued for at least 24 hours after completing the 50mg dose.

f Rasburicase (given at a flat dose of 6 mg IV x 1, or per institutional standards) should be administered per institutional guidelines for patients with elevated uric acid level at baseline (> ULN) as prophylaxis prior to the initial dose of venetoclax. For patients with a contraindication to rasburicase (i.e., glucose-6-phosphate dehydrogenase [G6PD] deficiency), the TLS risk-mitigation plan must be reviewed with the Overall PI.

Management of Other Toxicities

The following tables provide recommended guidelines for venetoclax dose reduction based on specific toxicities. Any subject who discontinues venetoclax due to toxicity may continue on the other study medications. Management not consistent with these guidelines should be discussed with the Overall PI:

Table 7: Dose Reduction Strategy for Patients Experiencing Non-Hematologic Toxicities on Venetoclax

Non-hematologic Toxicity Grade	Recommended Management/Next Dose for Venetoclax
≤ Grade 1 or 2	No change in dose
Grade 3	Hold* until ≤ Grade 1. At first occurrence, resume at same dose, no dose modification is required. At second and subsequent occurrences,** hold venetoclax and follow dose reduction guidelines in Table 5 when resuming treatment with venetoclax after resolution.
Grade 4	Permanently cease venetoclax therapy unless toxicity can be attributed to an alternative cause

^{*}Participants requiring a hold of >4 weeks of venetoclax due to a toxicity thought to be related to venetoclax should go off venetoclax therapy unless approved by the overall PI to remain on therapy.

With regard to specific nonhematologic toxicities, the recommended management for venetoclax-associated diarrhea is loperamide, dosed at 4 mg at first onset, followed by 2 mg with each loose bowel movement until diarrhea-free for 12 hours (maximum dosage: 16 mg/24 hours). Adjunct anti-diarrheal therapy is permitted and should be recorded when used.

Table 8: Dose Reduction Strategy for Patients Experiencing Neutropenia on Venetoclax

Neutropenia in				
patients on	Recommended Management/Next Dose for Venetoclax			
venetoclax				
≤ Grade 1 or	No change in dose			
Grade 2				
Grade 3 (ANC 500-999 cells/mm³)	Hold* until \leq Grade 2 or continue at current dose as long as growth factor is administered. (If venetoclax is continued, repeat ANC within 3 days and if still grade \geq 3, hold venetoclax until \leq Grade 2.) If not previously growth factor responsive, resume at one dose level lower, if indicated.**			
Grade 4	$ \text{Hold}^* $ until \leq Grade 3, then resume therapy at the same dose but with G-CSF			
(ANC <500	support. On second and subsequent occurrences, follow dose reduction			
cells/mm ³)	guidelines in Table 5 when resuming treatment.**			

*Participants requiring a hold of >4 weeks of venetoclax due to a venetoclax related therapy should go off protocol therapy unless approved by the overall PI to remain on therapy.

^{**}Participants requiring >3 dose reductions of venetoclax should go off venetoclax unless approved by the overall PI to remain on therapy.

^{**}Participants requiring >3 dose reductions of venetoclax should go off venetoclax unless with approval by the overall PI to remain on therapy.

Neutropenia in	
patients on	Recommended Management/Next Dose for Venetoclax
venetoclax	

At any time during the study, if the patient presents with febrile neutropenia, it is recommended that venetoclax be interrupted until resolution of the fever or infection. At the first occurrence, venetoclax may then be re-initiated at the same dose. At a second or later occurrence, consideration should be given to venetoclax dose reduction.

Growth factor support with filgrastim or pegfilgrastim may be utilized as necessary throughout the study and does not require holding venetoclax.

Table 9: Dose Reduction Strategy for Patients Experiencing Venetoclax-Related Hematologic Toxicities (excluding Neutropenia)

Venetoclax-related Hematologic Toxicities	Management/Next Dose for Venetoclax
\leq Grade 1, 2, or 3	No change in dose
Grade 4	Hold* until \leq Grade 3, unless the toxicity is thought to be due to a cause other than venetoclax. On first occurrence, venetoclax may be resumed at the same dose. On second and subsequent occurrences, follow the dose reduction guidelines in Table 5.**

*Participants requiring a hold of >4 weeks of venetoclax due to a venetoclax related therapy should go off protocol therapy unless approved by the overall PI to remain on therapy.

**Participants requiring >3 dose reductions of venetoclax should go off venetoclax unless with approval by the overall PI to remain on therapy.

